Official Title: Foot progression angle modification: an exploratory six-week intervention in people with knee osteoarthritis.

NCT Number: TBD

Document Date: March 24th, 2020

Study Protocol

Study Design

This parallel-group randomized clinical trial will consist of a 6-week gait modification intervention, delivered to two groups of older adults with medial compartment knee osteoarthritis (OA). The first group will receive a conventional delivery of gait modification (group name: SMOD), whereby they will practice the gait modification with a specific target (rotate foot 15° inward or outward relative to baseline). The second group will self-select the amount of modification they perform (group name: AMAC), guided by the instruction to “change foot rotation as much as is comfortable”. Foot rotation (toe-in or toe-out walking) is measured during the stance phase of walking as the angle of the foot’s long axis (heel to toe) relative to the direction of walking, and termed foot progression angle (FPA). In-lab and real-world gait analysis will be used to examine how the modification is learned, as well as the effect of the modification on biomechanical and clinical outcomes relevant to knee OA. In-lab assessment will be performed at baseline and a 7 week follow-up, while real-world assessment will be performed during the intervening weeks using wearable sensor technology (a custom sensorized shoe design). Both within-group and between-group comparisons will be made to identify differences in learning, difficulty, biomechanical, and clinical outcomes.

Primary Hypotheses

- H1: Participants receiving the specific FPA target will exhibit improved learning outcomes (e.g. lower error in performance, higher proportion of steps with $\geq 7^\circ$ of change from baseline FPA and lower variability) from week 1 to week 6, as measured during gait modification practice sessions, learning assessments, and during daily walking activity.
- H2: Participants receiving the self-directed FPA modification will exhibit improved learning outcomes (higher proportion of steps with $\geq 7^\circ$ of change from baseline FPA and lower variability) from week 1 to week 6, as measured during gait modification practice sessions, learning assessments, and during daily walking activity.
- H3: We expect FPA variability will be larger in the self-directed group, but both groups will exhibit a similar proportion of steps with $> 7^\circ$ of change from baseline FPA.

Secondary Hypotheses

- H4: Those in the self-directed modification group will exhibit smaller average changes in FPA compared to those in the conventional gait modification group. However, those in the self-directed modification group will report lower ratings of difficulty in performing the modification, compared to the specific-target gait modification group.
- H5: Both groups will exhibit improvements in biomechanical (e.g. knee adduction moment) and clinical outcomes (e.g. knee pain, physical function) at follow-up, compared to baseline.
- H6: Biomechanical (e.g. knee adduction moment) and clinical outcome (e.g. knee pain, physical function) change scores from baseline to follow up will not differ between groups.

Participants

Adults with knee OA will be recruited and randomized into two treatment arms. All eligible

participants will: 1) be 50 years of age or greater, 2) exhibit signs of tibiofemoral OA (a score of ≥ 2 on the Kellgren and Lawrence (KL) grading scale [1]) predominantly in the medial compartment, 3) self-reported knee pain $\geq 3 / 10$ on a numerical rating scale of pain (NRS; 0 = “no pain” and 10 = “worst pain imaginable”) during most days of the previous month, 4) are comfortable walking intermittently for 30 minutes, and 5) fit into the available sizes of sensorized shoes (sizes spanning US women’s 5 to men’s 13).

Exclusion criteria include: 1) any knee surgery or intraarticular injections within the past 6 months, 2) a history of joint replacement surgery or high tibial osteotomy, 3) current or recent (within 6 weeks) corticosteroid injections, 4) use of a gait aid, 5) currently on a wait list for joint replacement surgery or high tibial osteotomy, 6) any inflammatory arthritic condition, 7) any other conditions that may affect normal gait or participation in an aerobic exercise program, and 8) cannot attend all required appointments at UBC. Additionally, potential participants will undergo an initial gait screening similar to a recent study [2] (details are outlined below), with the goal of identifying participants who are capable of reducing their KAM magnitude when FPA is modified. This gait screen will examine both natural walking FPA and changes in knee load while walking with increased toe-in and toe-out. Those who do not elicit a reduction in KAM impulse $\geq 5\%$ when FPA is changed by 10° in either direction will be excluded from the study as they would be considered non-responders.

A total of 36 individuals will be recruited for this study, 18 in each group. Approximately 60% in each group will be female. The primary outcome measure of this study is the change in absolute FPA performance error (the difference between the performed and the targeted FPA), which is indicative of how ‘accurate’ the patient is when performing the modification. This outcome measure is only relevant to the SMOD group, who have a specific target for their modification; therefore, allowing an error value to be calculated. This outcome will be measured during immediate and delayed retention at week one compared to follow-up and will provide evidence of the extent to which motor learning has occurred. Previous FPA performance error during immediate retention testing after a six-week FPA modification resulted in a small effect (Cohens $d = 0.35$) [3]. We are also interested in exploring the clinical and biomechanical differences between the SMOD and AMAC gait modification groups; however, no study has previously compared these methods of gait modification. Therefore, we will be conservative and base our sample size calculation on the between-within interaction effect of a 2×4 (group = 2: SMOD vs AMAC; measure = 4: immediate and delayed retention tests at week 1 and follow up) repeated measures ANOVA with an effect size of $f = 0.175$ ($f = d / 2$). With power = 0.8 and alpha = 0.05, a total sample of 30 is required [4]. With a conservatively estimated attrition of 15%, we will recruit 36 participants total (18 per group).

Procedures

Recruitment and screening

Volunteers will be recruited via print and social media, and via our database of previous participants who have indicated interest in participating in future studies. Interested volunteers will be screened via phone, email, or our lab website by the study coordinator to assess inclusion and exclusion criteria. Those deemed preliminarily eligible will be invited to attend a gait screening appointment. Eligible participants who pass the gait screen will be referred for a radiographic assessment of their knees to confirm the presence of structural signs of knee OA.

Standing, semi-flexed posteroanterior radiographs of both knees will be taken. A trained assessor will grade all radiographs based on the KL criteria. Those passing all screening requirements will be invited to enroll in the study.

Gait screening

The gait screen will be performed using motion capture to measure self-selected FPA, joint angles, and joint moments during over-ground walking. Fifty-two retroreflective markers will be placed on the skin over boney landmarks and 14-high speed cameras (sample rate = 100 Hz) will track the positions of these markers in three dimensions. Additionally, two floor-mounted force platforms (sample rate = 2000 Hz) will measure ground reaction forces during walking. Natural walking trials across the 10m instrumented walkway will be performed first (one length equals one walking trial), followed by toe-in and toe-out walking. The latter will be guided verbally such that several walking passes are completed at a range of FPA magnitudes (small toe-in/out, medium toe-in/out, and large toe-in/out). The specific amount of change in FPA is not relevant, as long as a range of FPA magnitudes are recorded over the collected walking trials. These data will be used to determine whether the participant is a responder to FPA modification, and which direction (toe-in or toe-out) elicits the greatest response. The threshold of a 5% reduction in the knee adduction moment impulse (area under the knee adduction moment – time curve) with a 10° change in FPA will be used to determine response. For recruitment purposes, those who respond to either toe-in or toe-out ($\geq 5\%$ reduction with a 10° change in FPA) will be provided this FPA modification. For those who elicit response to both, the modification (toe-in or toe-out) with the greatest reduction per 10° of change in FPA will be used in the intervention. This cutoff value is conservative, allowing for some regression in response while still maintaining overall reduced KAM impulse. A 5% threshold was chosen as the average reduction in KAM impulse after a 16 week toe-out modification program was 4.7% [5]. These methods of screening for response to FPA change and personalizing the direction of FPA change were shown to improve biomechanical outcomes relative to a non-personalized approach [6, 7].

Baseline and follow-up data collection

An identical baseline and follow-up gait assessment, separated by seven weeks, will be conducted in the laboratory, and using both optical-motion capture and the sensorized shoe system. These assessments will include questionnaires, a timed stair climb, and gait analysis.

A) Patient reported outcomes and physical function

Questionnaires will be administered which will include an 11-point numerical rating scale (NRS) depicting average knee pain over the previous week where 0 = “no pain”, 10 = “worst pain imaginable”, the Knee Injury and Osteoarthritis Outcome Score (KOOS) [8], and the Pain Catastrophizing Scale [9]. Medical history, anthropometrics (height, body mass etc.), age, and symptom duration will also be recorded by the assessor. The timed stair climb (a measure of physical function) will be performed on a 12-stair flight. Participants will be instructed to “climb as quickly, but safely as possible” [10]. Two repetitions will be performed, and the fastest time will be used.

B) Gait analysis

A total of 52 reflective markers (45 lower limbs; 7 upper limbs) will be affixed to the skin bilaterally over key anatomical landmarks as is standard in our laboratory [11]. Fourteen high-

speed cameras (sample rate = 100 Hz) will track the positions of these markers and two floor-embedded force platforms (sample rate = 2000 Hz) will measure ground reaction forces. Five passes along a 10m instrumented walkway will be performed barefoot and then shod. Walking speed at the baseline assessment will be measured using two timing gates placed at a known distance along the walkway. At follow-up, participants will first complete five walking passes at a self-selected speed and then be constrained to walk within $\pm 5\%$ of their baseline walking speed, due to the impact of walking speed on joint moments. After over-ground walking, a 5-minute treadmill walk will be performed while wearing a pair of sensorized shoes (details included below). This will provide a controlled measurement of FPA from the sensorized shoe for comparison with FPA measured at each practice session and during daily at-home walking.

A 1-minute dual-task assessment will be performed immediately after the 5-minute treadmill walking trial, according to established methods [12]. Briefly, a single letter or category will be provided at the start of the 1-minute period. The instructions will be to continue walking naturally while simultaneously dictating as many words as possible (word-list generation) that start with the letter or belong to the category. The number of correct words dictated will be recorded.

Stair ascent and descent will be performed while wearing the sensorized shoes. This will take place at a building nearby the laboratory (5-minute walk) because of the availability of continuous linear sets of stairs for multiple flights. This allows the use of the sensorized shoe for measuring FPA during stair ascent and descent. These FPA data will be compared with transfer test data (details included below) examined at several points throughout the intervention. These same shoes will be provided to the participant to measure real-world FPA during at-home and community walking.

Sensorized shoes

A custom inertial sensor consisting of a 3-axis accelerometer (signal range: $\pm 4g$), gyroscope ($\pm 500^\circ/s$), and magnetometer ($\pm 1200\mu T$), sampling data at 100 Hz will be embedded in the sole of the shoe. A previously published custom sensor fusion algorithm [13], programmed into a microcontroller, calculates the FPA in real time and stores it on a microSD card for later extraction. The sensorized shoe design and algorithm has been validated during treadmill [14] and over-ground walking [15] with excellent validity and reliability (absolute error = 1.7° and intraclass correlation coefficients > 0.9).

Randomization

Once deemed eligible and baseline data collection is complete, each participant will be randomized to either the SMOD or AMAC group. Randomization will be performed using an *a priori* block-stratified approach based on sex and KL grade. A predetermined randomization matrix will be computed [16] by a team member not involved in testing or the intervention. Group allocations will be stored in opaque envelopes, which will be opened in a sequential manner after baseline testing and before the first practice session. The group allocation will be communicated to the study trainer via email.

Gait modification intervention

Both groups will attend six practice sessions conducted weekly, which will last approximately 1 hour each. Walking practice will be conducted on a treadmill with a full-length mirror placed

directly in front of the treadmill. The SMOD group will be guided to increase their FPA by 15° in either the toe-in or toe-out direction (determined by the gait screen). A line of tape will be aligned on the mirror according to the target FPA, as we have done previously [5, 17]. This mirror-based method of providing a target for the FPA modification was shown to be similarly effective when compared to feedback delivered using an expensive real-time motion capture system, but with significantly greater clinical feasibility. The AMAC group will be instructed to increase their FPA by “as much as is comfortable”. The mirror will be provided during practice sessions; however, no tapeline will be placed. The amount of time spent with the feedback (mirror) visible will be progressively reduced (faded feedback) across the six weekly practice sessions in order to reduce the reliance on feedback [18]. Before and immediately after the practice sessions, the participant will perform a warm-up and cool-down walk while wearing the sensorized shoes (10-minute outdoor standardized walking loop). This will provide a repeatable non-laboratory-based measure of FPA. Both groups will be encouraged to practice their gait modification at any opportunity during their daily at-home walking. Practice sessions will be led by a kinesiologist with experience delivering gait modification interventions.

Learning will be measured during 1) practice, 2) immediate and delayed retention tests, 3) dual-task tests, 4) transfer tests, and 5) during at-home/community walking. Each test (2-4) will last 1 min and be collected at each practice session. For the SMOD group, the absolute performance error (absolute error = |performed FPA – target FPA|), FPA variability, and the proportion of steps with >7° of change from baseline FPA will be measured using the sensorized shoe. For the AMAC group, FPA variability and the proportion of steps with >7° of change from baseline FPA will be measured. Retention tests will occur immediately before (starting at practice session 2) and after practice bouts. The participant will be asked to perform their gait modification as accurately as possible for 1 minute. Dual-task testing will be performed identically to the baseline assessment described above; however, the participant will be asked to simultaneously perform their gait modification. Lastly, transfer testing will be performed during stair ascent and descent in the same manner as the baseline assessment.

During each practice session, participants will be asked to rate their knee pain at the beginning, middle, and end of the session using an 11-point numerical rating scale (0 = “no pain” and 10 = “worst pain imaginable”). At the end of the sessions, they will be asked to rate the difficulty in achieving their FPA modification during that practice period using an 11-point numerical rating scale (0 = “not difficult” and 10 = “most difficult/unable to perform”).

An instructional booklet will be provided which outlines details of how to care for and use the sensorized shoes while at home and in the community. Participants will track daily walking volume, walking times on each day, daily knee pain using an NRS (e.g. overall pain, pain during walking), non-walking exercise activities, and any adverse events related to their knees or walking. Additionally, an 11-point numerical rating scale will be used to report weekly confidence in how accurately the FPA modification was performed (0 = “no confidence at all/unable to perform” and 10 = “completely confident”) and difficulty in performing the modification (0 = “not difficulty” and 10 = “most difficult/unable to perform”). A minimum of 10-minutes of daily walking will be requested to ensure enough data for the analysis.

Data processing and analysis

Marker-based motion capture data (as collected during the baseline and follow-up assessments) will be processed using commercially available software and using standard techniques our research group has established [5, 11, 19, 20]. Sensorized shoe data captured during the baseline and follow-up gait assessment, practice sessions, and at-home or community walking will be processed using custom MATLAB scripts. A trained research assistant, blinded to group allocation, will perform all data processing and analysis.

References

- [3] Richards R, van der Esch M, van den Noort JC, Harlaar J. The learning process of gait retraining using real-time feedback in patients with medial knee osteoarthritis. *Gait Posture.* 2018;62:1-6.

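### H1 and H2 count lower foot progression angle variability in daily walking as better learning, but over all home steps it also reflects how often and how far the foot is rotated

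*Protocol*

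**What the plan says.** Under Primary Hypotheses, H1 (the specific-target group, SMOD) and H2 (the self-directed group, AMAC) each list two shared signs of improved learning: a higher proportion of steps at least 7° from baseline, and "lower variability) from week 1 to week 6, as measured during gait modification practice sessions, learning assessments, and during daily walking activity". H1 adds lower error. H3 is a between-group statement: "We expect FPA variability will be larger in the self-directed group", with a similar proportion of steps beyond 7°.

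The section Gait modification intervention lists five settings for measuring learning, the last being "and 5) during at-home/community walking". FPA variability is an outcome in both groups; for the self-directed group, "For the AMAC group, FPA variability and the proportion of steps with >7° of change from baseline FPA will be measured". In retention tests the participant is told to perform the modification for the full minute. For home walking the instruction is looser: "Both groups will be encouraged to practice their gait modification at any opportunity during their daily at-home walking". The only volume request is this: "A minimum of 10-minutes of daily walking will be requested to ensure enough data for the analysis".

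Neither document gives a formula for FPA variability, a rule for which home steps enter it, or a way to tell modified from natural steps. The SAP does not name variability. Its between-group model takes FPA change from baseline, in the lab and at home, as the learning outcome.

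**The concern.** One word, variability, covers two different quantities. When every step is meant to be modified, the spread of FPA shows how consistently the new gait is produced. When some steps are modified and others are natural, the spread also contains the distance between the two gaits, weighted by how evenly they are mixed. The companion criterion in H1 and H2, a rising proportion of steps past 7°, itself presupposes such a mixture in daily walking.

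At stake is the sign of a learning result. A participant who uses the modification more at week 6 than at week 1 may satisfy one criterion and fail the other because of the same progress. If H3 is also examined with home data, a second problem arises. The arms are expected to differ in the size of their modification, so home variability can differ between arms for reasons unrelated to control.

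**Working it through.** The plan gives no figure for FPA variability, so there is none to reproduce. Its one computed figure, 30 participants inflated to 36, rests on retention tests and is not involved here.

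**Inputs from the documents**
- Size of the SMOD modification, D = 15°: "The SMOD group will be guided to increase their FPA by 15° in either the toe-in or toe-out direction".
- AMAC modification expected to be smaller, with no value given (H4): "Those in the self-directed modification group will exhibit smaller average changes in FPA compared to those in the conventional gait modification group".
- Share of home steps that are modified, p: not stated, so any value from 0 to 1.

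**Assumptions**
- Step-to-step SD in natural walking, s0, and in modified walking, s1: base case 3° for both, then unequal values.
- AMAC modification: 8° in the example, with 5° and 10° as the range.
- Variability is the SD over all home steps.

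**Formula.** For a mixture of two walking modes whose means differ by D:

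SD² = p(1−p)D² + p·s1² + (1−p)·s0²

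With s0 = s1 = s this is s² + p(1−p)D². The maximum is at p = 0.5 + (s1² − s0²)/(2D²): 0.50 for equal SDs, and 0.54 for s0 = 3°, s1 = 5°, D = 15°. It comes later when D is small and modified steps are much less consistent (0.66 for 3°, 5° and D = 7°).

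**SD (degrees) by share of modified steps**

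| D, s0, s1 | 0 | 10% | 25% | 50% | 75% | 90% | 100% |
|---|---|---|---|---|---|---|---|
| 15, 3, 3 | 3.00 | 5.41 | 7.15 | 8.08 | 7.15 | 5.41 | 3.00 |
| 10, 3, 3 | 3.00 | 4.24 | 5.27 | 5.83 | 5.27 | 4.24 | 3.00 |
| 5, 3, 3 | 3.00 | 3.35 | 3.70 | 3.91 | 3.70 | 3.35 | 3.00 |
| 15, 3, 5 | 3.00 | 5.55 | 7.43 | 8.56 | 7.95 | 6.61 | 5.00 |

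Simulating 400,000 steps for the first row gives 3.0, 7.16, 8.08, 7.16 and 3.0 at 0, 25, 50, 75 and 100%.

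**Week 1 to week 6, D = 15°, s = 3°.** With equal SDs, growing use raises the SD whenever the two shares add to less than 1.
- 10% to 40%: √(0.09×225 + 9) = 5.41 to √(0.24×225 + 9) = 7.94, a rise.
- 30% to 70%: 7.50 to 7.50, no change.
- 50% to 90%: 8.08 to 5.41, a fall.

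In the first case the expected proportion of steps past 7° goes from about 11% to 40%. (About 99.6% of modified and 1% of natural steps pass; 0.1×0.996 + 0.9×0.01 = 0.108 and 0.4×0.996 + 0.6×0.01 = 0.404.) One criterion is met and the other fails. Better control need not offset this: if s1 falls from 5° to 3° while use grows from 10% to 40%, the SD still rises, from 5.55 to 7.94.

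**H3, if home data are used.** Equal use in both arms; SMOD D = 15°, s0 = s1 = 3°; AMAC D = 8°, s0 = 3°, s1 = 5°.

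| Use | 25% | 50% | 75% | 90% | 95% | 100% |
|---|---|---|---|---|---|---|
| SMOD | 7.15 | 8.08 | 7.15 | 5.41 | 4.44 | 3.00 |
| AMAC | 5.00 | 5.74 | 5.74 | 5.40 | 5.22 | 5.00 |

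AMAC's modified steps are the less consistent, yet its home SD is smaller until about 90% use. With an AMAC SD of 4° in both modes, its figure at 50% is √(0.25×64 + 16) = 5.66. The curves cross where (15² − D²)(1−p) = 5² − 3² = 16, with D the AMAC modification. That gives p = 0.92, 0.90 and 0.87 for D of 5°, 8° and 10°.

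**The case against.** The strongest reply is that variability is simply undefined. The protocol never says it is an SD pooled over all home steps. Participants log walking times and processing is left to custom scripts, so a walk-level or step-to-step measure would also fit the text. This stands in part: the size of the effect depends on pooling. But the hypotheses fix the direction of benefit for daily walking while nothing isolates modified steps, so the criterion as written allows the misleading calculation.

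Several stronger readings are tempting, and the documents do not support them.
- *Home variability always rises with adoption.* It does not. Past about half of steps it falls, which is the direction H1 and H2 expect, and the plan gives no adoption shares for week 1 or week 6.
- *Never using the modification scores as good learning.* H1 and H2 concern change from week 1 to week 6. A constant non-user shows no fall in variability and no rise in the proportion, so is not scored as improved. With equal within-mode SDs, non-use also only ties with full adoption for the lowest SD.
- *H3 treats lower home variability as better.* H3 names no setting and does not call lower variability better, and the SAP's between-group model does not name variability. The reversal matters only if home data are used for H3.
- *The primary outcome is compromised.* Under Participants, the stated primary outcome is the change in absolute error in retention tests, in SMOD only. Those tests are instructed throughout.

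**Conclusion.** The concern holds for H1 and H2 in daily walking. Computed over all home steps, FPA variability depends on frequency of use and size of modification as well as on control, and its relation to use is not monotone. It therefore cannot carry a lower-is-better reading. At the 15° target with a 3° within-mode SD, the same kind of progress can raise it by 2.5° (10% to 40% use), leave it unchanged (30% to 70%) or lower it by 2.7° (50% to 90%). At a 5° modification the 10% to 40% rise is only from 3.35° to √(0.24×25 + 9) = 3.87°. For H3 the effect is conditional on home data being used; the expected order can then reverse at intermediate use, for example 8.1° against 5.7° at 50%.

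The within-mode SDs, the shares of modified steps and the AMAC modification size are assumptions. That home walking mixes both modes is an inference from the loose home instruction, though a well-supported one. The fault is confined to one learning measure in one of five settings, in a trial titled exploratory. It should be corrected because it can give a learning result the wrong sign.

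**What to change.** In H1 to H3 and in the SAP, limit the variability hypotheses to instructed walking: practice, retention, dual-task and transfer tests. State how FPA variability is calculated there. Keep the proportion of steps with at least 7° of change as the learning outcome for home walking, and report home variability descriptively beside it, with no direction of benefit attached.

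Filtering home data to bouts whose median change exceeds 7° would not rescue the measure. A bout with 55% modified steps at D = 15° and s = 3° passes that filter with an SD of √(0.2475×225 + 9) = 8.0°, close to the maximum. The filter would also tend to remove more AMAC bouts, since H4 expects smaller changes there, and so would select differently by arm.

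The cost is wording in two documents and one fewer home-walking learning outcome. No new data are needed, and the sample size does not change.

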Official Title: Foot progression angle modification: an exploratory six-week intervention in people with knee osteoarthritis.

NCT Number: TBD

Document Date: Mar 24th, 2020

Statistical Analysis Plan

Statistical analyses will be performed by an independent statistician. Means and standard deviations will be calculated for each outcome measure and baseline demographic characteristic. Baseline demographic data (e.g. age, body mass index, disease severity) will be examined for between-group differences using unpaired two-tailed t-tests. For all statistical analyses, alpha will be set to 0.05. Any multiple pairwise comparisons will be adjusted using the Bonferroni correction method.

Data will be assessed for sphericity, homoscedasticity, and normality using Mauchley's test, residual versus predicted plots, and quantile-quantile plots. Homoscedasticity and normality assumptions will be confirmed using Levene's test and Shapiro-Wilk's test, respectively. Sphericity assumption violations will be corrected for using the Greenhouse Geisser approach. Violations of homoscedasticity will be corrected for by bootstrapped model parameters. If normality is not met, a non-parametric test will be used.

Primary Hypotheses:

Repeated measures analyses of variance (ANOVA) will be performed to examine the within-group changes in learning outcomes over the six-week intervention. Between-group differences will be examined using a two-way mixed ANOVA, with the repeated measure being the learning outcome (foot progression angle change from baseline during in-lab and at-home walking) and the between-subject factor being group assignment (SMOD vs AMAC).

Secondary Hypotheses:

Biomechanical (knee joint moments), clinical (NRS knee pain, KOOS pain, symptoms, and physical function scores), and difficulty (difficulty of performing the FPA modification) change scores will be examined using an analysis of covariance (ANCOVA) with significant between-group baseline demographic group differences and baseline outcome values included as covariates.

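### H6 predicts no difference between arms, but the SAP plans only a test for a difference; H3's similar-proportion clause has no between-group analysis clearly assigned

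*Protocol*

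**What the plan says.** Two of the protocol's predictions are of sameness. H6 (Secondary Hypotheses) says that biomechanical and clinical "change scores from baseline to follow up will not differ between groups". The second clause of H3 (Primary Hypotheses) says that "both groups will exhibit a similar proportion of steps" changed by more than 7° from baseline.

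For the secondary outcomes the SAP says that "change scores will be examined using an analysis of covariance (ANCOVA) with significant between-group baseline demographic group differences and baseline outcome values included as covariates". For the learning outcomes it says: "Between-group differences will be examined using a two-way mixed ANOVA". The repeated measure in that model is described as "foot progression angle change from baseline during in-lab and at-home walking". The significance rule is general: "For all statistical analyses, alpha will be set to 0.05". If normality fails, an unnamed non-parametric test replaces the model.

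Neither document gives an equivalence or non-inferiority margin, a rule based on a confidence interval, or a statement of what a non-significant between-group result will mean.

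**The concern.** ANCOVA and mixed ANOVA F-tests ask whether the data are incompatible with zero difference. Failing to reject zero does not show that the difference is small. When the hypothesis itself is that the arms do not differ, and a difference test is the only analysis, the one outcome compatible with the hypothesis is p > 0.05. That outcome becomes more likely as the trial gets smaller or noisier.

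What is at stake is the practical question of whether self-directed modification does as well as the 15° target. The protocol's own reasoning makes some difference plausible. H4 predicts a smaller average FPA change in the self-directed arm. The gait screen admits only people whose knee adduction moment impulse falls by at least 5% with a 10° change. If both hold, the arms might be expected to differ somewhat in knee load, yet H6 predicts that they will not.

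**Working it through.** **Inputs from the documents.** The protocol (Participants) requires 30 in total, so 30/2 = 15 per arm. The attrition step reproduces: 30/0.85 = 35.3, so 36 recruited, 18 per arm. The 30 was derived for a group-by-measure interaction on retention tests (f = 0.175), not for showing similarity. It also depends on a repeated-measures correlation that is not stated: about 0.68 to 0.70 gives 30, and 0.5 gives 46. That is a separate matter; only the 15 per arm is used here. Alpha is 0.05.

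**Assumptions.** The documents give no SD, correlation or margin. Differences below are in SDs of the change score, with equal variances at baseline and follow-up, the baseline value as the only covariate, and a baseline-to-follow-up correlation r of 0.3 to 0.8.

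**Step 1: unadjusted comparison of change scores.**
- 95% CI half-width = t(0.975, 28) × √(2/15) = 2.048 × 0.365 = 0.75 SD.
- Noncentrality = d × √(15/2): 1.37 at d = 0.5 and 2.19 at d = 0.8.
- Power is 26% and 56%, so p > 0.05 occurs in 74% and 44% of trials.
- If all 18 per arm complete, p > 0.05 still occurs in 69% and 36%, with a half-width of 0.68 SD.

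**Step 2: the planned ANCOVA.** With outcome SD σ, the change score has SD σ√(2(1−r)) and the ANCOVA residual has SD σ√(1−r²). Their ratio is k = √((1+r)/2). The half-width is t(0.975, 27) × √(2/15) × k = 2.052 × 0.365 × k = 0.749k, and the noncentrality is (d/k) × √(15/2).

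**Step 3: a similarity rule, if one were used.** With identical arms, the last two columns give the simulated probability that the 90% CI lies wholly inside the margin.

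| Analysis | k | 95% half-width (SD) | p > 0.05 at 0.5 SD | p > 0.05 at 0.8 SD | 90% CI inside ±0.5 SD | inside ±0.8 SD |
|---|---|---|---|---|---|---|
| Unadjusted | 1 | 0.75 | 74% | 44% | 1% | 38% |
| ANCOVA, r = 0.3 | 0.806 | 0.60 | 63% | 26% | 8% | 68% |
| ANCOVA, r = 0.5 | 0.866 | 0.65 | 67% | 32% | 4% | 59% |
| ANCOVA, r = 0.8 | 0.949 | 0.71 | 71% | 40% | 1% | 46% |

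Even an observed difference of exactly zero would leave true differences of up to 0.60 to 0.71 SD unexcluded.

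**Step 4: H3.** The protocol lists the proportion of steps as a learning outcome in both arms. The SAP's between-group model specifies FPA change from baseline as the repeated measure. These are different variables, so no between-group analysis is explicitly assigned to the proportion. If the mixed ANOVA were extended to it, it would still be a difference test. The table does not apply to H3, because a repeated-measures comparison depends on correlations that the documents do not give.

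**The case against.** The strongest reply is that the harm is inferred. A reader might conclude that the sponsor will declare the arms similar whenever p > 0.05. Neither document says so. The protocol describes the between-group comparisons as a search for differences, and its sample-size text speaks of exploring them; a difference test suits that aim. This stands, and the point is limited to what the plan leaves open: it offers no other route to a conclusion on H6.

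It is also fair that the unadjusted figures are not the planned analysis. Baseline adjustment helps, and larger differences would often be found: a true 0.8 SD difference is detected in 56% of trials even unadjusted, and in about 60% to 74% with adjustment. It would be wrong to say that the trial returns p > 0.05 whether or not the arms differ.

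The scale needs care. At r = 0.7 the ANCOVA half-width is 2.052 × 0.365 × √(1 − 0.49) = 0.54 in SDs of the raw outcome. In change-score SDs, where H6 is framed, the same interval is 0.749 × √(1.7/2) = 0.69. The smaller number is not a gain in precision.

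Finally, the trial is titled exploratory, H6 is secondary, and the primary outcome (FPA performance error) concerns the fixed-target arm only. That limits the consequence, but it also favours estimation over a prediction of no difference.

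**Conclusion.** The point holds for H6. As written, the only planned result that could be taken to support it is a non-significant ANCOVA, which at about 15 completers per arm would occur in roughly 63% to 71% of trials when the true difference is 0.5 change-score SD, and in 26% to 40% when it is 0.8 SD. These figures rest on equal variances and an assumed correlation of 0.3 to 0.8.

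For H3 the defect is different. A reader might infer that the mixed ANOVA tests the similar-proportion clause, but the SAP does not name that outcome. The clause has no clearly assigned between-group analysis, and a difference test would carry the same limit in kind, though its size cannot be computed from the documents. Because H3 is listed as primary, the gap should be closed. The issue should be corrected before analysis; it does not undermine the trial's design.

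**What to change.** - **Protocol:** reword H6 and the second clause of H3 as estimation aims, that is, to estimate the between-group difference and its precision.
- **SAP:** name the proportion of steps with more than 7° of change as a between-group outcome. For every outcome under H6 and H3, report the adjusted between-group difference with its 95% CI, and say in outcome units which differences the interval excludes. State that p > 0.05 will not be reported as absence of a difference or as similarity.
- **If a similarity claim is kept:** fix a margin for each outcome before data lock and require the 90% CI to lie inside it. State the probability of success under the planned ANCOVA over a range of correlations. For H6 with identical arms this is about 1% to 8% at a margin of 0.5 change-score SD, and 46% to 68% at 0.8 SD.

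The cost is wording plus one named outcome. The H6 intervals come from the model already planned, and no extra participants, visits or measurements are needed. The downside for the sponsor is that the trial can no longer claim equality by default.
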